10.4.7 Follow-up of subjects after study participation has ended

Following this study, the subject will return to their eye care professional for their routine eye care.

11 ADVERSE EVENTS AND DEVICE DEFICIENCIES

11.1 General Information

An AE is any untoward medical occurrence, unintended disease or injury, or untoward clinical signs (including abnormal laboratory findings) in subjects, users, or other persons, whether or not related to the investigational medical device (test product). Refer to the Glossary of Terms for categories of AEs and SAEs.

Figure 11-1 **Categorization of All Adverse Events**

[figure not shown]
[figure not shown]

Figure 11-2 **Categorization of All Serious Adverse Events**

Specific Events Relevant to this Protocol

In addition to reporting all AEs (serious and non-serious) meeting the definitions, the Investigator must report any occurrence of the following as an SAE:

Cumulative (at any visit during the study) Serious Adverse Events:

- Cystoid macular edema
- Hypopyon
- Endophthalmitis
- Lens dislocation
- Pupillary block
- Retinal detachment
- Secondary surgical intervention (excluding posterior capsulotomy)

Persistent (still present at conclusion of study) Serious Adverse Events:

- Corneal stromal edema
- Cystoid macular edema
- Iritis
- Elevated IOP requiring treatment

Any other potentially sight-threatening event may also be considered serious based on the judgment of the Investigator and should be reported appropriately as delineated in Section [11.3](#).

11.2 Device Deficiencies

A device deficiency may or may not be associated with subject harm (i.e., ADE or SADE); however, not all ADEs or SADEs are due to a device deficiency. The Investigator should determine the applicable category for the identified or suspect device deficiency and report any subject harm separately. Examples of device deficiencies include the following:

- Failure to meet product specifications (e.g., incorrect IOL power)
- IOL and delivery system defect
- Broken IOL optic

- Broken IOL haptic
- Scratched IOL optic
- Unsealed device packaging
- Suspect product contamination (IOL, delivery system)
- Lack of effectiveness
- Injector issue
- Cartridge damage
- Delivery system issue

11.3 Monitoring for Adverse Events

At each visit, after the subject has had the opportunity to spontaneously mention any problems, the Investigator should inquire about AEs by asking the standard questions shown below and report as applicable:

- “Have you had any health problems since your last study visit?”
- “Have there been any changes in the medicines you take since your last study visit?”

In addition, changes in any protocol-specific parameters and/or questionnaires evaluated during the study are to be reviewed by the Investigator. Any untoward (unfavorable and unintended) change in a protocol-specific parameter or questionnaire response that is clinically relevant, in the opinion of the Investigator, is to be reported as an AE. These clinically relevant changes will be reported regardless of causality.

11.4 Procedures for Recording and Reporting

AEs are collected from the time of informed consent. Any pre-existing medical conditions or signs/symptoms present in a subject prior to the start of the study (i.e., before informed consent is signed) are not considered AEs in the study and should be recorded in the Medical History section of the eCRF.

In addition, aqueous cells and flare, corneal edema, raised IOP and superficial punctate keratitis are examples of early post-operative findings that are typically observed following ocular surgery. These are not considered AEs if they can be reasonably expected to resolve within a week and not result in any untoward long term visual outcome impact.

For each recorded event, the ADEs and SAEs documentation must include: date of occurrence, severity, treatment (if applicable), outcome, and assessments of the seriousness and causality. In addition, the Investigator must document all device deficiencies reported or observed with study test (Clareon / Clareon Toric) and control (Eyhance / Eyhance Toric) products on the Device Deficiency eCRF. The site must submit all available information on ADEs, SAEs, and device deficiencies to the Study

Sponsor immediately as follows:

- All SAEs must be reported immediately (within 24 hours) of the Investigator's or site's awareness.
- ADEs that do not meet seriousness criteria and device deficiencies must be reported within 10 calendar days of the Investigator's or site's awareness.
- A printed copy of the completed *Serious Adverse Event and Adverse Device Effect and/or Device Deficiency* eCRF must be included with product returns.
- Additional relevant information after initial reporting must be entered into the eCRF as soon as the data become available.
- Document any changes to concomitant medications on the appropriate eCRFs.
- Document all relevant information from Discharge Summary, Autopsy Report, Certificate of Death etc., if applicable, in narrative section of the Adverse Device Effect (for related AEs) and Serious Adverse Event eCRF.

Note: Should the EDC system become non-operational, the site must complete the appropriate paper Serious Adverse Event and Adverse Device Effect and/or Device Deficiency Form. The completed form is emailed to the Study Sponsor at [contact] according to the timelines outlined above; however, the reported information must be entered into the EDC system once it becomes operational.

Any AEs and device deficiencies for the control IOLs and any non-study marketed devices/products (i.e., Eyhance/Eyhance Toric IOLs and OVDs) will be considered and processed as spontaneous (following the post-market vigilance procedures) and should be communicated to the device's/product's manufacturer as per local requirements. Any AEs and device deficiencies with the test or control IP should still be reported in EDC and can enter in the comment the other manufactures product if applicable.

Study Sponsor representatives may be contacted for any protocol related question and their contact information is provided in the MOP that accompanies this protocol.

Further, depending upon the nature of the AE or device deficiency being reported, the Study Sponsor may request copies of applicable portions of the subject's medical records. The Investigator must also report all AEs and study IP device deficiencies that could have led to a SADE according to the requirements of regulatory authorities or IRB/IEC.

11.5 Intensity and Causality Assessments

Where appropriate, the Investigator must assess the intensity (severity) of the AE based on medical judgment with consideration of any subjective symptom(s), as defined below:

Intensity (Severity)

Mild: An AE is mild if the subject is aware of but can easily tolerate the sign or symptom.

Moderate: An AE is moderate if the sign or symptom results in discomfort significant enough to cause interference with the subject's usual activities.

Severe: An AE is severe if the sign or symptom is incapacitating and results in the subject's inability to work or engage in their usual activities.

For every AE in the study, the Investigator must assess the causality (Related or Not Related to the medical device or study procedure). An assessment of causality will also be performed by Study Sponsor utilizing the same definitions, as shown below:

Causality

Related: An AE classified as related may be either definitely related or possibly related where a direct cause and effect relationship with the medical device or study procedure has not been demonstrated, but there is a reasonable possibility that the AE was caused by the medical device or study procedure.

Not Related: An AE classified as not related may either be definitely unrelated or simply unlikely to be related (i.e., there are other more likely causes for the AE).

The Study Sponsor will assess the AEs and may upgrade the Investigator's assessment of seriousness and/or causality. The Study Sponsor will notify the Investigator of any AEs that is upgraded from non-serious to serious or from unrelated to related.

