1 GLOSSARY OF TERMS

Names of Test Products	Throughout this document, test products Clareon Aspheric Hydrophobic Acrylic IOL and Clareon Toric Aspheric Hydrophobic Acrylic IOL (Models SY60WF; CNW0T3, CNW0T4, CNW0T5, CNW0T6) will be referred to as Clareon/Clareon Toric IOLs.
Name of Comparator Products	Throughout this document, comparator products TECNIS Eyhance/Eyhance Toric II IOL with TECNIS Simplicity Delivery System (Models DIB00; DIU150, DIU225, DIU300, DIU375) will be referred to as Eyhance/Eyhance Toric IOLs.
Adverse Device Effect (ADE)	
Adverse events related to the use of an investigational medical device (test product) or control product.
 
Note: This definition includes adverse events resulting from insufficient or inadequate instructions for use, deployment, implantation, installation, or operation; any malfunction; and use error or intentional misuse of the investigational medical device (test product) or comparator product.

Adverse Event (AE)	
Any untoward medical occurrence, unintended disease or injury, or untoward clinical signs (including abnormal laboratory findings) in subjects, users or other persons, whether or not related to the investigational medical device (investigational product).
 
Note: For subjects, this definition includes events related to the test product, the control product, or the procedures involved. For users or other persons, this definition is restricted to events related to the test product
 
Requirements for reporting Adverse Events in the study can be found in Section 11.

Anticipated Serious Adverse Device Effect (ASADE)	An effect which by its nature, incidence, severity, or outcome has been identified in the risk assessment.

Clinical Investigation Plan (CIP)	
The document(s) stating the rationale, objectives, design, and prespecified analysis, methodology, organization, monitoring, conduct, and record-keeping of the clinical investigation.
 
Note: The protocol and other documents referenced in the protocol (for example, the Statistical Analysis Plan, the Manual of Procedures, the Deviations and Evaluability Plan, and the Protocol Monitoring Plan) comprise the CIP.

Clinical Investigation Report (CIR) / Clinical Study Report	
The document describing the design, execution, statistical analysis, and results of a clinical investigation. The Clinical Investigation Report is synonymous with the Clinical Study Report.

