Product Complaint	Any oral, electronic, or written communication that alleges deficiencies related to the identity (labeling), quality, durability, reliability, safety, effectiveness, or performance of a marketed product, including failure of the product, labeling, or packaging to meet specifications, whether or not the product is related to or caused the alleged deficiency. A complaint may allege that an adverse event or medical device malfunction has occurred.
Randomized Subject	Any subject who is assigned a randomized treatment.
Serious Adverse Device Effect (SADE)	Adverse device effect that has resulted in any of the consequences characteristic of a serious adverse event.
Serious Adverse Event (SAE)	Adverse event that led to any of the following: 
• Death.• A serious deterioration in the health of the subject, that either results in:
a) a life-threatening illness or injury 
Note: Life-threatening means that the individual was at

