5.3.1 Adverse Events

The applicable definition of an Adverse Event (AE) is in the study protocol. The number and percentage of all ocular adverse events will be tabulated for any event and by MedDRA Preferred Term by treatment. An eye with multiple ocular AEs of the same preferred term is only counted once toward the total of this preferred term. The number of events will also be presented. Adverse events related to the study IOL are referred to as adverse device effects.

Additionally, adverse events associated with SSI, specifically with preferred terms indicating secondary IOL intervention, will be summarized by relatedness to the study device by treatment. For SSIs, the number of events is not applicable and therefore will not be presented.

Adverse events will be summarized in the following tables, by treatment:

1. All Adverse Events (Serious and Non-Serious Combined)
 - a. Ocular
 - b. Nonocular
2. All Adverse Device Effects
 - a. Ocular
 - b. Nonocular
3. All Serious Adverse Events (including Serious Adverse Device Effects)
 - a. Ocular
 - b. Nonocular
4. Secondary Surgical Interventions (SSIs)
3. Subject/Eye Listings
 - a. Non-serious Ocular
 - b. Non-serious Nonocular
 - c. Serious Ocular
 - d. Serious Nonocular
 - e. SSIs

In addition, listings of treatment-emergent and non-treatment emergent adverse events will be provided separately. The treatment-emergent AE listings will include, but are not limited to, the following variables: IOL model, subject identification number, age, sex, surgery eye (first or second implanted eye), eye (OD or OS), days from surgery, AE duration, and corresponding AE details.

Individual subject listings will be provided for AEs that occur after signing informed consent but prior to exposure to investigational product (i.e., non-treatment emergent). The non-treatment emergent AE listings will include, but are not limited to, the following variables: subject identification number, age, sex, eye (if applicable), days prior to planned surgery, duration, and corresponding AE details.

A listing of all SSIs will also be presented and will include, but is not limited to, the following variables: IOL model, subject identification number, age, sex, eye, days from surgery, duration, and corresponding AE details

Ocular AEs and SSIs will also be summarized by toric and non-toric lenses for all eyes combined only.

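### Protocol 11.5 rates causality to device or procedure in one call, but the ADE table and the SSI summary need relatedness to the study lens alone

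*Protocol*

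**What the plan says.** - **Protocol 11.5** sets the causality question: "For every AE in the study, the Investigator must assess the causality (Related or Not Related to the medical device or study procedure"). The Related category is met when "there is a reasonable possibility that the AE was caused by the medical device or study procedure". It defines no separate device-related and procedure-related categories. The sponsor also rates causality under the same definitions and may upgrade the investigator's rating.
- **Protocol 11.4** says that discharge, autopsy and similar information belongs "in narrative section of the Adverse Device Effect (for related AEs) and Serious Adverse Event eCRF".
- **Protocol glossary** defines an ADE as "Adverse events related to the use of an investigational medical device (test product) or control product". Its note extends this to "adverse events resulting from insufficient or inadequate instructions for use, deployment, implantation, installation, or operation", and to malfunction and use error. A serious ADE (SADE) is an "Adverse device effect that has resulted in any of the consequences characteristic of a serious adverse event".
- **SAP 5.3.1** states: "Adverse events related to the study IOL are referred to as adverse device effects". It plans an ADE table by treatment, ocular and nonocular. AEs whose preferred terms indicate a secondary IOL intervention are to be summarized by device relatedness. SADEs appear inside a table of "All Serious Adverse Events (including Serious Adverse Device Effects").

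**The concern.** The rating that is collected is broader than the rating the tables need. Every subject in both arms has cataract surgery, so an event caused only by the operation meets the Related definition in 11.5 whatever the lens did. The protocol recognizes the distinction elsewhere: the glossary note on adverse events lists the test product, the control product and the procedures as separate sources. Section 11.5 merges them again.

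The ADE table is the output that attributes harm to a particular lens. If procedure-only events can enter it, its counts stop meaning what the SAP says they mean, and two sites could classify the same event differently. The label also drives conduct. Under 11.4 a non-serious ADE must be reported within 10 calendar days, and under 11.6 the sponsor's own products linked to product-related AEs should be returned.

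**Working it through.** No formula applies, and neither document states a figure that depends on this point. The check sets the texts side by side and follows one event through them.

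**1. What is recorded and what is needed**

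| Item | Source | Scope of relatedness |
|---|---|---|
| Causality call on each AE | Protocol 11.5 | device or procedure, combined |
| Label on the ADE form | Protocol 11.4 | related AEs, cause not specified |
| ADE definition | Protocol glossary | use of the test or control product |
| ADE definition | SAP 5.3.1 | study IOL |
| Split of SSI events | SAP 5.3.1 | study device |

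The first two rows are wider than the last three.

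**2. Is there a rule linking them?** I looked in the protocol glossary, in Protocol 10.2.13 and 11.1 to 11.6, and in SAP 5.3.1. None says how a combined Related call becomes related to the IOL. Sponsor review does not supply one, because it uses the same definitions and describes only upgrades.

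**3. One event traced.** Take a cystoid macular edema that the investigator attributes to the surgery alone. Protocol 5.3 lists it as a possible postoperative event, and 11.1 requires it to be reported as an SAE at any visit.
- Under 11.5 it is Related, because the procedure is a sufficient cause.
- By the label in 11.4, a related AE goes to the ADE form.
- By the glossary and by SAP 5.3.1, it is not an ADE.
- If it is treated as an ADE, it also takes the SADE label, since a SADE is a serious ADE.
- In the all-SAE table it counts once either way.

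The documents thus point two ways on whether this event is an ADE, and agree on the SAE count.

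**4. Which events are exposed.** Protocol 11.4 says that early findings such as cells and flare, corneal edema, raised IOP and superficial punctate keratitis are not AEs if they can be expected to resolve within a week with no lasting effect on vision. Those cannot become ADEs. The exposed events are surgical complications that do qualify as AEs: cystoid macular edema, and iritis or corneal stromal edema still present at study end (11.1).

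**5. Direction of the error.** Let D be the eyes with a device-related event and P the further eyes with only a procedure-related event rated Related. If the combined call feeds the table, an arm shows D + P instead of D. The count can only rise. Where P is similar in the two arms, the difference in counts is about the same on average but more variable, and the ratio moves toward 1. No value of P can be taken from the documents.

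**The case against.** The strongest reply is that the data capture may already be right. The AE eCRF and the Manual of Procedures are not among the documents, and Figures 11-1 and 11-2, which categorize adverse events, are not shown. The sentence in 11.5 can be read as asking for two judgements, one on the device and one on the procedure. The planned SSI split suggests that a device-specific field exists. The glossary and SAP 5.3.1, applied literally, exclude a procedure-only event. The label in 11.4 comes from a bullet about where to put narrative information, so it is weak evidence of a routing rule.

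All of this stands as a limit on the claim. A reader might infer that ordinary cataract-surgery complications do enter the ADE table. The documents show only that they may. A reader might also infer that the SSI split cannot be produced. That does not follow either, since the eCRF may hold the field.

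The reply also notes that the safety analysis is descriptive (SAP 5.2) and that the lenses are compared in many other ways. All AEs, IOL observations, posterior capsule opacification, capsulotomy, device deficiencies and IOL position change are shown by treatment with no causality rating. That is correct, so the ADE table should not be described as the only safety comparison between the lenses.

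The reply does not remove the mismatch itself. The visible text states one definition of Related, and it is not the one the ADE table needs. If sites can read 11.5 in two ways, the ADE count depends on the reader. The ambiguity matters more because causality is judged by a delegated investigator (10.2.13), while masking covers only the subject and the VA assessor (9.4).

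**Conclusion.** The point holds as a mismatch of definitions. Protocol 11.5 gives a combined device-or-procedure rating, the ADE table and the SSI split in SAP 5.3.1 need a device rating, and the available text does not connect them. Procedure-only complications that qualify as AEs may therefore be counted as device effects of the implanted lens.

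The reach is the ADE table, the SADE label and the SSI split by relatedness. A reader might expect an inflated SADE table as well, but the SAP lists none: SADEs sit within the all-SAE table, which takes every SAE whatever its cause. The other by-treatment safety summaries and the primary BCDVA analysis are not touched.

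No numerical size can be given, because any rate of procedure-related events would be an assumption without support in the documents. The conclusion assumes that the unseen eCRF, manual and figures do not already separate the two ratings. If they do, what remains is a wording fault in 11.5 and 11.4.

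**What to change.** - **Protocol 11.5 and the AE eCRF:** replace the combined call with two separate yes/no ratings, (a) related to the study IOL or its delivery system and (b) related to the surgical procedure. The sponsor's assessment should use the same two ratings.
- **Protocol 11.4 and SAP 5.3.1:** state that ADEs, the SADE label and the SSI summary by relatedness are derived from rating (a), identically in both arms. Show events with only rating (b) separately as procedure-related.

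The cost is one extra eCRF field, the wording changes, and re-rating by query of AEs already entered, preferably before database lock. If the eCRF already records the two ratings, only the wording changes.

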11.6 Return Product Analysis

Study Sponsor representatives and their contact information are provided in the MOP that accompanies this protocol.

Alcon study products associated with device deficiencies and/or product related AEs should be returned and must include the Complaint # which will be provided by Study Sponsor after the case is entered in the Study Sponsor's Global Product Complaint Management System (GPCMS).

11.7 Unmasking of the Study Treatment

Masked information on the identity of the assigned medical device should not be disclosed during the study. Refer to Section 9.4 "Treatment Masking" of the protocol. If the treatment code needs to be broken in the interest of subject safety, the Investigator is encouraged to contact an appropriate Study Sponsor representative prior to unmasking the information if there is sufficient time. Dependent upon the individual circumstances (i.e., medical emergency), the code may be broken prior to contact with the Study Sponsor. The Study Sponsor must be informed of all cases in which the code was broken and of the circumstances involved. Additionally, the Study Sponsor may be required to unmask the information in order to fulfill expedited regulatory reporting requirements.

11.8 Follow-Up of Subjects with Adverse Events

The Investigator is responsible for adequate and safe medical care of subjects during the study and for ensuring that appropriate medical care and relevant follow-up procedures are maintained after the study.

The Investigator should provide the Study Sponsor with any new safety information (which includes new AEs and changes to previously reported AEs) that may affect the safety evaluation of the device. For AEs that are unresolved/ ongoing at time of subject exit from study, any additional information received at follow-up should be documented in the eCRFs up to study completion (i.e., database lock).

All complaints received after this time period will be considered and processed as spontaneous (following the post-market vigilance procedures) and should be communicated to the medical device's manufacturer as per local requirements.

The Investigator should also report complaints on non-Alcon products directly to the manufacturer as per the manufacturer's instructions or local regulatory requirements.

